### **8 Data Quality Monitoring and Storage**

#### **8.1 Data Quality Monitoring**

Data quality will be reviewed remotely using front-end range and logic checks at the time of data entry and back-end monitoring of data using a secure web platform for building and managing online databases (REDCap) to generate data reports. We will perform routine monitoring to examine the completeness and accuracy of informed consent documents for study participants, documentation of eligibility criteria, and the completeness of study outcome collection.

#### **8.2 Data Storage**

Data will be entered into a secure online database. All data will be maintained in the secure online database (REDCap) until the time of study publication. At the time of publication, a de-identified version of the database will be generated.

## 9 Risk Assessment

### 9.1 Potential Risk to Participants

Anticoagulation strategy and monitoring tools vary within and across institutions. There are no randomized controlled trials evaluating safety or comparing the effect of different strategies on clinical outcomes. In this trial, two anticoagulation strategies are proposed: 1. Low intensity anticoagulation administered at doses and frequencies commonly used for DVT prophylaxis and 2. Moderate intensity anticoagulation titrated to a PTT goal of 40-60 seconds or an Anti-Xa level of 0.2-0.3 IU/mL. This first strategy of low intensity anticoagulation (a strategy congruent with usual DVT prophylaxis) is being studied in this trial with the goal of decreasing life-threatening bleeding, a common and potentially catastrophic complication during V-V ECMO. This strategy is not the standard of care. The second strategy of moderate intensity reflects usual care at our institution for patients receiving V-V ECMO at our institution; however, it has been documented that patients with a contraindication to anticoagulation (e.g. recent surgery) can be safely managed on V-V ECMO without any anticoagulation. Therefore, regardless of treatment arm, patients randomized in this study will receive an anticoagulation strategy that they may have received even if they were not included in the study and would, therefore, not experience any additional risks beyond usual care.

A potential risk to patients participating in this study involves the collection of protected health information (PHI) and the risk of loss of confidentiality. In order to limit the associated risks, the minimum amount of PHI necessary for study conduct will be collected. After collection, the data will be stored in a secure online database (REDCap) only accessible by the investigators. REDCap tools will be used to ensure that the PHI that is collected is only visible to investigators at the healthcare system where the patient is enrolled. To protect participant privacy, REDCap tools will be used to ensure that only deidentified data can be exported for use during the analyses.

#### 9.1.1 Potential Risks of Receiving Low Intensity Anticoagulation for Patients Receiving V-V ECMO

Receiving ECMO carries risks of thromboembolism, hemolysis, consumptive coagulopathies, and circuit thrombosis. Moderate intensity anticoagulation may decrease these risks. Potential risks of receiving low intensity anticoagulation instead of moderate intensity anticoagulation include:

- 1) Thromboembolism – pulmonary embolism, DVT, ischemic strokes, and cardiac thrombus. The risk of thromboembolism applies to all patients receiving venovenous ECMO regardless of anticoagulation strategy but may be increased in patients who receive low intensity anticoagulation only.

2) Hemolysis – venovenous ECMO causes shear stress and mechanical trauma to red blood cells, which leads to risks of hemolysis. All patients receiving venovenous ECMO are at risk for hemolysis. If anticoagulation reduces the risk of hemolysis, a less intense anticoagulation strategy may increase the risk of hemolysis.

3) Consumptive coagulopathy – the coagulation system is activated by the foreign surfaces of the ECMO circuit. This process can lead to damage and consumption of clotting factors and platelets, leading to coagulation system dysfunction. Though it has never been demonstrated, a less intense anticoagulation strategy, may exacerbate risks of consumptive coagulopathy and dysregulation of the coagulation system. Ultimately this could generate higher risks of either bleeding, clotting, or both.

2) Circuit thrombosis – fibrin and thrombus can accumulate throughout the components of the ECMO circuit (generally the oxygenator) over time due to the non-biologic surfaces of the device and turbulent areas of blood flow. The burden of thrombus may either gradually or acutely worsen requiring a controlled or emergent circuit component exchange. When a circuit component acutely fails to operate, and during any circuit component exchange, the patient may be inadequately supported by ECMO temporarily and may experience clinical compromise, including hypoxemia, acidemia, hypotension, symptomatic bradycardia, and other cardiac arrhythmias. During the majority of circuit exchanges the physiologic derangements are transient and without deleterious consequences; nevertheless, in the most severe circumstances, these may lead to cardiac arrest. All patients receiving ECMO are at risk for requiring a circuit or circuit component exchange, and circuit or circuit component exchange are frequently required for patients receiving V-V ECMO regardless of anticoagulation strategy. Compared to moderate intensity anticoagulation, a strategy of low intensity anticoagulation could increase the risk of circuit thrombosis, but based on available data, this is unknown.

### **9.1.2 Potential Risks of Receiving Moderate Intensity Anticoagulation for Patients Receiving V-V ECMO**

One potential risk to participating in this study is receiving the moderate intensity anticoagulation strategy rather than the low intensity anticoagulation strategy. Moderate intensity could increase the risk of life-threatening bleeding relative to low intensity anticoagulation. Because moderate intensity anticoagulation is the standard strategy for patients receiving V-V ECMO at this institution, the moderate intensity anticoagulation strategy does not represent any risk beyond the risks of receiving V-V ECMO as part of usual care.

## **9.2 Minimization of Risk**

Federal regulations at 45 CFR 46.111(a)(1) require that risks to participants are minimized by using procedures which are consistent with a sound research design. This study protocol incorporates numerous design elements to minimize risk to patients that meet this human subject protection requirement. Both low intensity and moderate intensity anticoagulation (Heparin and Bivalirudin) have been approved by the Food and Drug Administration and have been used in clinical practice during ECMO for decades with an established safety profile. Experience treating patients receiving venovenous ECMO with both low intensity and moderate intensity anticoagulation strategies has been reported in the literature. Data suggest, but do not prove, that both strategies are safe. To mitigate risk introduced by either strategy we exclude from the study patients with known allergy to heparin, patients with known or suspected active bleeding or thromboembolism and patients at higher than usual risk of bleeding or thromboembolism. Given the concerns regarding increased risk of thromboembolism among

patients with COVID-19, we also exclude patients with a positive SARS-CoV-2 test within 21 days of screening or for whom the treatment team has a high clinical suspicion for COVID-19. Furthermore, the trial specifically excludes all patients for which the treating clinicians believe a specific anticoagulation strategy is required, so all enrolled participants will be assessed safe for either treatment group by treating clinicians. Finally, at any time during the study, the treatment team may change the anticoagulation strategy if and when it is determined to be necessary for patient safety. The study protocol includes daily monitoring for protocol adherence and adverse events during the period of the study intervention.

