#### Exclusion criteria:

1. Patient is pregnant
2. Patient is a prisoner
3. Patient is < 18 years old
4. Patient underwent ECMO cannulation greater than 24 hours prior to screening
5. Presence of an indication for systemic anticoagulation:
  - a. Ongoing receipt of systemic anticoagulation
  - b. Planned administration of anticoagulation for an indication other than ECMO
  - c. Presence of or plan to insert an arterial ECMO cannula
6. Presence of a contraindication to anticoagulation:
  - a. Active bleeding determined by treating clinicians to make anticoagulation unsafe
  - b. Major surgery or trauma less than 72 hours prior to randomization
  - c. Known history of a bleeding diathesis
  - d. Ongoing severe thrombocytopenia (platelet count < 30,000)
  - e. History of heparin induced thrombocytopenia (HIT)
  - f. Heparin allergy

7. The treating clinician determines that the patient's risks of thromboembolism or bleeding necessitate a specific approach to anticoagulation management during V-V ECMO

**Consent:** Patients or their surrogates will provide written informed consent to study personnel.

**Randomization:** After enrollment, patients will be randomized in a 1:1 ratio to initiation of either low intensity anticoagulation or moderate intensity anticoagulation. The randomization will be performed electronically through REDCap using permuted randomized blocks of two, four, and six.

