## 4 Study Population, Inclusion and Exclusion Criteria

### 4.1 Study Population

All adult patients receiving V-V ECMO will be screened for eligibility. Patients meeting all inclusion and no exclusion criteria will be approached for consent. To be eligible for enrollment, the patient must meet all inclusion criteria and no exclusion criteria at the time of screening and randomization. Screening and randomization must be accomplished within 24 hours of ECMO cannulation.

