**5.2 Determination of Eligibility**

All patients meeting inclusion criteria will be screened for eligibility and assigned a deidentified study identification number. If a patient appears to meet all inclusion criteria and no exclusion criteria, the site investigator or delegate will approach the treating clinician to ask permission to approach the patient or Legally Authorized Representative (LAR) to confirm eligibility, discuss potential study recruitment, and proceed with informed consent.

For all excluded patients, including refusal by the treating clinician or patient/surrogate, a small number of de-identified variables will be collected including month and year the patient met screening criteria, patient location, and reason(s) patient was excluded.

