### **5.4 Enrollment**

Patients who meet inclusion criteria but no exclusion criteria and provide written informed consent will be enrolled immediately after written informed consent has been obtained *and* eligibility has been confirmed with the treating physician. Patients who initially meet all inclusion criteria and no exclusion criteria at the time of screening but develop a change in clinical status that prohibits receipt of either study treatment prior to randomization (i.e. development of one or more exclusion criteria or death) will be excluded from study participation and prospectively recorded.

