#### **Baseline Variable Collection:**

- Date and time of hospital admission
- Date and time of ICU admission
- Date and time of intubation (if applicable)
- Age
- Assigned gender at birth
- Height
- Weight
- Body mass index
- Self-reported race
- SAPS II score
- Physiologic parameters at randomization (e.g. heart rate, blood pressure, respiratory rate), receipt of vasopressors (agent, dose)
- Measures of mental status and delirium at randomization [e.g. Richmond Agitation-Sedation Score (RASS), Confusion Assessment Method for the ICU (CAM-ICU), Glasgow Coma Scale (GCS)]
- Indication for ECMO
- Respiratory support immediately prior to ECMO cannulation (e.g. nasal cannula, high flow nasal cannula, non-invasive ventilation, or invasive ventilation)
- Fraction of inspired oxygen immediately prior to ECMO cannulation
- Positive end-expiratory pressure immediately prior to ECMO cannulation
- History of chronic lung disease
- History of lung transplantation
- History of thromboembolism
- History of stroke
- History of major bleeding event
- Chronic receipt of anticoagulation
- Receipt of anticoagulation at the time of randomization (e.g. aspirin, clopidogrel, warfarin, direct-acting oral anticoagulants) in the 7 days prior to randomization
- Active medical problems at randomization (e.g. sepsis, septic shock, acute renal failure requiring renal replacement therapy)
- Most recent complete blood count, creatinine, PTT, Anti-Xa, and INR values prior to randomization

- Most recent arterial blood prior to ECMO cannulation
- Date and time of ECMO cannulation
- ECMO configuration at randomization
- Number and location of ECMO cannula sites at randomization
- Manufacturer and model of ECMO circuit at randomization
- Manufacturer and model of oxygenator at randomization
- ECMO settings at randomization (blood flow, revolutions per minute, sweep gas flow, fraction of delivered oxygen)

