### 7.2.3 Feasibility Outcomes

- Number of patients screened per month
- Number of patients who are eligible per month
- The specific exclusion criteria met (for any patient ineligible for enrollment)
- Reasons for “missed” enrollments (e.g. unavailability of research staff, refusal of clinical team to allow randomization, patient refusal of informed consent)
- Number of patients enrolled per month
- Adherence to the assigned anticoagulation strategy
- Separation between groups in anticoagulation treatment received
- Time from ECMO cannulation to randomization

- Duration of the intervention period, defined as the time from randomization to the first of: diagnosis of a major bleeding event, diagnosis of a thromboembolic event, placement of an arterial ECMO cannula, decannulation from ECMO, or death

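### Section 9.2 says patients with recent or suspected COVID-19 are excluded, but neither exclusion list contains that criterion

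*Combined protocol and SAP*

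**What the plan says.** Section 9.2 sets out how risk to participants is kept down. Among the measures it states, in the present tense, that "we also exclude patients with a positive SARS-CoV-2 test within 21 days of screening". The sentence adds patients for whom the treatment team has a strong clinical suspicion of COVID-19, and gives thromboembolism risk as the reason. The next sentence adds a further safeguard: "Furthermore, the trial specifically excludes all patients for which the treating clinicians believe a specific anticoagulation strategy is required".

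Section 4.1 says how eligibility is decided: "To be eligible for enrollment, the patient must meet all inclusion criteria and no exclusion criteria at the time of screening and randomization". The exclusion criteria are listed twice, in the Trial Summary and in section 4.3, and the two lists match item for item. They cover pregnancy, prisoner status, age, time since cannulation, an indication for systemic anticoagulation (three sub-items), a contraindication to anticoagulation (six sub-items), and a final item 7. Item 7 applies when the treating clinician judges that the patient's "risks of thromboembolism or bleeding necessitate a specific approach to anticoagulation management during V-V ECMO". Neither list mentions COVID-19 or SARS-CoV-2.

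The treating clinician is also consulted twice on the way to enrollment. Under section 5.2 "the site investigator or delegate will approach the treating clinician to ask permission to approach the patient" or their representative, and under section 5.4 enrollment follows once consent is obtained and "eligibility has been confirmed with the treating physician".

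**The concern.** A risk section should describe protections that the eligibility criteria actually deliver. Here it describes one that they do not.

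- **Participant protection.** Section 9.2 singles out these patients for thromboembolism risk. Under 4.3 they can be randomized, and so assigned to low intensity anticoagulation, the strategy for which section 9.1.1 says that same risk may be higher.
- **Accuracy of the risk assessment.** Section 9.4 judges the risks reasonable on the strength of the assessment that precedes it. One stated element of that assessment is not implemented.
- **Feasibility results.** Section 7.2.3 includes "Number of patients who are eligible per month" and the exclusion criteria that ineligible patients met. Both differ according to whether the COVID-19 rule is applied, and section 5.1 lists three sites that could read the protocol differently.

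**Working it through.** There is no figure to reproduce. The check compares the texts and makes simple counts.

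**Step 1: what 9.2 requires.** The exclusion has two limbs: (a) a positive SARS-CoV-2 test within 21 days of screening, and (b) high clinical suspicion on the part of the treatment team. Limb (a) is a fixed rule that needs a test result and a date. Limb (b) is a clinical judgement about a diagnosis.

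**Step 2: look for either limb in the exclusion lists.** Separately stated criteria in each list:

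- single items 1, 2, 3, 4 and 7: 5
- sub-items 5a to 5c: 3
- sub-items 6a to 6f: 6
- total: 5 + 3 + 6 = 14

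| Place | Criteria stated | Naming COVID-19 or SARS-CoV-2 |
|---|---|---|
| Trial Summary, exclusion criteria | 14 | 0 |
| Section 4.3 | 14 | 0 |
| Section 9.2 | not a list | both limbs |

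Neither of the two inclusion criteria concerns COVID-19.

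**Step 3: look elsewhere.** Section 9.2 is the only place that mentions COVID-19. Section 11 repeats the thromboembolism safeguard, but only as exclusion of patients with active thromboembolism or thought to be at high risk of it. The baseline list in section 7.1 has 32 entries, and 0 of 32 is a SARS-CoV-2 test result or date. "Indication for ECMO" or the entry for active medical problems might reveal COVID-19 incidentally, but neither would show whether the 21-day rule had been applied.

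**Step 4: ask whether another criterion implies it.** Item 7 is the nearest. It excludes a patient only if the treating clinician concludes that a specific anticoagulation approach is needed. Take a patient who tested positive 10 days before screening and whose clinician is content with either strategy. Item 7 is not triggered and no other listed criterion applies, so under 4.1 and 4.3 the patient is eligible. Under 9.2 the patient is excluded. Section 9.2 also treats the two as distinct, because it introduces clinician judgement with *Furthermore* after the COVID-19 sentence.

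**Step 5: rule out an artefact.** The sentence is current body text, not an amendment log. It runs across a page break but reads continuously, and nothing is blacked out.

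**The case against.** The best case on the other side accepts the mismatch and disputes its weight.

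- **Clinician safeguards cover most of it.** Item 7 names thromboembolism risk, and the treating clinician is consulted before approach and again before enrollment. Limb (b) is itself a treating-team judgement, so the contrast between a fixed rule and a judgement is sharp only for the 21-day limb. This stands, and it lowers the likely number of affected patients. It does not supply the 21-day rule, and confirming eligibility means confirming it against lists that omit the criterion.
- **The baseline list is weak evidence.** It describes enrolled patients and is not a screening checklist. It also has no entry for pregnancy, prisoner status or heparin allergy, which are undoubtedly exclusions. This stands. The 0-of-32 count shows only that use of the rule could not be verified from the baseline data; it does not show that the rule is absent.
- **The feasibility counts are defined.** Section 4.1 points to the criteria and the two lists agree, so if every site screens from 4.3 the counts are consistent. This is fair. In that case, though, they describe a wider population than the one described in 9.2.
- **Section 9.4 does not depend on this sentence.** The reasons it gives are long clinical use and data suggesting that either strategy is safe, and 9.2 contains other safeguards. Nothing shows that the conclusion would fail. The point is only that it refers back to an assessment containing an inaccurate statement.
- **The trial is a small descriptive pilot.** It enrolls at most 30 patients and runs no inferential tests. That limits the numbers but does not make the safety statement true.

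**Conclusion.** The contradiction holds and should be corrected. Section 9.2 states an exclusion that appears in 0 of 14 criteria in each of the two lists that decide eligibility, so a patient can be correctly enrolled under 4.3 and yet be described as excluded in 9.2.

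The number of patients concerned cannot be calculated, since the document gives no rate of recent or suspected COVID-19 among patients on V-V ECMO. No effect on sample size, power or the analysis population is claimed.

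The conclusion assumes only that screeners work from the stated criteria, as 4.1 directs. The document does not show which text is intended. The sentence in 9.2 may be left over from another version, or the criterion may have been omitted from the lists. Either way one of the passages is wrong. This review takes no position on whether patients with COVID-19 should be enrolled.

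**What to change.** Make section 9.2, section 4.3 and the Trial Summary agree, with the same COVID-19 criterion in all three or in none. The sponsor decides which is intended.

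- **If the criterion is kept:** put both limbs into 4.3 and the Trial Summary and add it to the recorded exclusion reasons. Capturing the SARS-CoV-2 test result and date at screening is not needed to remove the contradiction, but without it use of the 21-day rule cannot be verified.
- **If it is not kept:** delete the sentence from 9.2 and confirm that the conclusion in 9.4 still holds without it.

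The cost is a wording amendment and, if the criterion is kept, one more exclusion reason and one screening entry for the test result and date. No extra patients are needed and the analysis does not change.

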### **9.3 Potential Benefit**

Study participants may or may not receive any direct benefits from their participation in this study. Participants who are randomized to the moderate intensity anticoagulation group are expected to receive the anticoagulation strategy that they would receive were they to choose not to participate in the study; thus, this group is not expected to receive a direct benefit. If administration of low intensity anticoagulation improves clinical outcomes among adults receiving V-V ECMO, the participants randomized to this group may directly benefit.

### **9.4 Risk in Relation to Anticipated Benefit**

Federal regulations at 45 CFR 46.111 (a)(2) require that “the risks to subjects are reasonable in relation to anticipated benefits, if any, to subjects, and the importance of the knowledge that may reasonably be expected to result.” Based on the preceding assessment of risks and potential benefits, the risks to participants are reasonable in relation to anticipated benefits. Various anticoagulation strategies for patients receiving V-V ECMO have been used in clinical practice for decades. Although data do not prove safety or superiority between these strategies there are data to suggest either strategy is safe and potentially effective.

